### **12.3 Electrocardiogram**

A 12-lead resting ECG will be obtained at the visits indicated in the Schedule of Assessments ([Table 9-1](#)).

At screening, the Investigator will examine the ECG traces for signs of cardiac disease that could exclude the patient from the study. An assessment of normal or abnormal will be recorded and if the ECG is considered abnormal, the abnormality will be documented on the eCRF. ECGs will be repeated if clinically significant abnormalities are observed or artifacts are present.

Additionally, a 12-lead resting ECG will be obtained in order to assess QTcF on Cycle 1 Day 1 prior to study drug infusion and on Cycle 1 Day 3 ( $48 \pm 2$  hours after the end of the study drug infusion on Day 1). If the QTcF increases above the upper limit of normal or if it increases on Day 3 more than 10 msec greater than at baseline, then repeat ECG testing for QTcF assessment should be performed prior to and  $48 \pm 2$  hours after then next OBI-999 dose.

## **12.4      Laboratory Assessments**

Laboratory assessment samples ([Table 12-1](#)) are to be obtained at designated visits as detailed in the Schedule of Assessments ([Table 9-1](#)).

**Table 12-1      Laboratory Assessments**

Hematology	Serum chemistry	Urine analysis (dipstick)

 
• Hemoglobin (Hb)
 
• Hematocrit
 
• Mean corpuscular hemoglobin (MCH)
 
• Mean corpuscular hemoglobin concentration (MCHC)
 
• Mean corpuscular volume (MCV)
 
• Platelet count
 
• Red blood cell (RBC) count
 
• White blood cell (WBC) count with differential
 
	
 
• Albumin
 
• Alanine aminotransferase (ALT)
 
• Alkaline phosphatase (ALP)
 
• Aspartate aminotransferase (AST)
 
• Blood urea nitrogen (BUN) or Urea
 
• Bicarbonate
 
• Creatinine
 
• Creatine kinase
 
• Electrolytes (Na, K, Cl, Ca, P, Mg)
 
• Glucose
 
• Lactate dehydrogenase (LDH)
 
• Total bilirubin
 
• Total protein
 
• Uric acid
 
	
 
• Appearance
 
• Blood
 
• pH
 
• Protein
 
• Glucose
 
• Ketones
 
• Nitrite
 
• Leukocyte esterase
 
• Specific gravity
 
• Urine human chorionic gonadotropin (HCG) (pre-menopausal females only)
 
• Urobilinogen
 
• Bilirubin
 
• Microscopic, as needed
 

Coagulation	Pregnancy test	

 
• Prothrombin time (PT)
 
• International Normalized Ratio (INR)
 
• Activated partial thromboplastin time (aPTT)
 
	To be performed on all female patients of child-bearing potential at the screening visit and early termination visit.	

Routine safety laboratory testing will be performed at the local laboratory following the laboratory's guidelines. Pharmacokinetic samples, ADAs, and biomarkers will be analyzed at a central laboratory facility. Urine samples will be analyzed by dipstick, and a microscopic analysis will be performed if the results of dipstick indicate abnormalities to be further investigated. All laboratory reports must be reviewed, signed, and dated by the Investigator and/or Sub-investigator. The signature and date can be wet ink or electronic. Any laboratory test results considered by the Investigator to be clinically significant should be considered an AE (clinically significant AEs include those that require an intervention). Clinically significant abnormal values occurring during the study will be followed until repeat test results return to normal, stabilize, or are no longer clinically significant.

## **12.5 Adverse Events**

### **12.5.1 Adverse Events**

An AE is any symptom, physical sign, syndrome, or disease that either emerges during the study period or worsens during the study, regardless of the suspected cause of the event. All medical and psychiatric conditions (except those related to the indication under study) present at screening will be documented in the medical history eCRF. Changes in these conditions and new symptoms, physical signs, syndromes, or diseases should be noted on the AE eCRF during the rest of the study. Clinically significant laboratory abnormalities should also be recorded as AEs. Surgical procedures that were planned before the patient enrolled in the study are not considered AEs if the conditions were known before study inclusion; the medical condition should be reported in the patient's medical history.

Patients will be instructed to report AEs at each study visit. All AEs are to be followed until resolution or until a stable clinical endpoint is reached.

Each AE is to be documented on the eCRF with reference to date of onset, duration, incidence, severity, relationship to study drug, action taken with study drug, treatment of event, and outcome. Furthermore, each AE is to be classified as being serious or non-serious. Changes in AEs and resolution dates are to be documented on the eCRF.

For the purpose of this study, treatment emergent AEs will be collected starting from the time the patient receives the first dose of study drug (from Cycle 1 Day 1) until 28 days after the last dose of study drug. Follow-up of the AE, even after the date of therapy discontinuation, is required if the AE persists until the event resolves or stabilizes at a level acceptable to the Investigator.

Specific guidelines for classifying AEs by intensity (Grade) and relationship to study drug are given in Table 12-2 and [Table 12-3](#). The severity of AEs will be graded according to the NCI CTCAE version 5.0 (Grades 1 to 5).

When changes in the intensity of an AE occur more frequently than once a day, the maximum intensity for the event should be noted.

**Table 12-2 Classification of Adverse Events by Intensity (NCI CTCAE Grade)**

**Mild (Grade 1):** An event that is easily tolerated by the patient, causing minimal discomfort, and not interfering with everyday activities.

**Moderate (Grade 2):** An event that is sufficiently discomforting to interfere with normal everyday activities.

**Severe (Grade 3):** An event that prevents normal everyday activities.

**Life-threatening (Grade 4)**

**Death (Grade 5)**

**Table 12-3      Classification of Adverse Events by Relationship to Study Drug**

Unrelated: This category applies to those AEs that are clearly and incontrovertibly due to extraneous causes (disease, environment, etc.).
Unlikely: This category applies to those AEs that are judged to be unrelated to the test drug, but for which no extraneous cause may be found. An AE may be considered unlikely to be related to study drug if or when it meets 2 of the following criteria: (1) it does not follow a reasonable temporal sequence from administration of the test drug; (2) it could readily have been produced by the patient's clinical state, environmental or toxic factors, or other modes of therapy administered to the patient; (3) it does not follow a known pattern of response to the test drug; or (4) it does not reappear or worsen when the drug is re-administered.
Possibly: This category applies to those AEs for which a connection with the test drug administration appears unlikely but cannot be ruled out with certainty. An AE may be considered possibly related if or when it meets 2 of the following criteria: (1) it follows a reasonable temporal sequence from administration of the drug; (2) it could not readily have been produced by the patient's clinical state, environmental or toxic factors, or other modes of therapy administered to the patient; or (3) it follows a known pattern of response to the test drug.
Probably: This category applies to those AEs that the Investigator feels with a high degree of certainty are related to the test drug. An AE may be considered probably related if or when it meets 3 of the following criteria: (1) it follows a reasonable temporal sequence from administration of the drug; (2) it could not be reasonably explained by the known characteristics of the patient's clinical state, environmental or toxic factors, or other modes of therapy administered to the patient; (3) it disappears or decreases on cessation or reduction in dose (note that there are exceptions when an AE does not disappear upon discontinuation of the drug, yet drug-relatedness clearly exists; for example, as in bone marrow depression, fixed drug eruptions, or tardive dyskinesia); or (4) it follows a known pattern of response to the test drug.
Definitely: This category applies to those AEs that the Investigator feels are incontrovertibly related to test drug. An AE may be assigned an attribution of definitely related if or when it meets all of the following criteria: (1) it follows a reasonable temporal sequence from administration of the drug; (2) it could not be reasonably explained by the known characteristics of the patient's clinical state, environmental or toxic factors, or other modes of therapy administered to the patient; (3) it disappears or decreases on cessation or reduction in dose and recurs with re-exposure to drug (if re-challenge occurs); and (4) it follows a known pattern of response to the test drug.

### 12.5.2    Serious Adverse Events

An AE is considered “serious” if in the view of either the Investigator or Sponsor, it meets one or more of the following criteria:

- Is fatal
- Is life-threatening
- Results in inpatient hospitalization or prolongation of existing hospitalization
- Results in a persistent or significant incapacity or substantial disruption of the ability to conduct normal life functions

- Is a congenital anomaly/birth defect

Other important medical events that may not be immediately life-threatening or result in death or hospitalization, based upon appropriate medical judgment, are considered SAEs if they are thought to jeopardize the patient and/or require medical or surgical intervention to prevent one of the outcomes defining a SAE. Since SAEs are critically important for the identification of significant safety problems, it is important to take into account both the Investigator's and the Sponsor's assessment. If either the Sponsor or the Investigator believes that an event is serious, the event must be considered serious and evaluated by the Sponsor for expedited reporting.

### **12.5.3 Serious Adverse Event Reporting**

An SAE occurring during the study from the first dose of study treatment (Cycle 1 Day 1) to within 28 days of stopping the treatment must be reported to the contracted CRO and will be communicated to the Sponsor. Any such SAE due to any cause, whether or not related to the study drug, must be reported within 24 hours of occurrence or when the Investigator first becomes aware of the event. The Investigator must enter all SAE information into the electronic data capture (EDC) (preferred method), electronic mail (SAE Report Form), dedicated fax line or telephone line (emergency), to the Sponsor/contracted CRO.

If the Investigator contacts the contracted CRO by telephone, then a written report must follow within 24 hours and is to include a full description of the event and sequelae in the format detailed in the SAE reporting form.

The event must also be recorded on the standard AE eCRF. Preliminary reports of SAEs must be followed by detailed descriptions later on, including clear and anonymized photocopies of hospital case reports, consultant reports, autopsy reports, and other documents when requested and applicable. SAE reports must be made whether or not the Investigator considers the event to be related to the investigational drug.

Appropriate remedial measures should be taken to treat the SAE, and the response should be recorded. Clinical, laboratory, and diagnostic measures should be employed as needed in order to determine the etiology of the problem. The Investigator must report all additional follow-up evaluations to the contracted CRO within 10 calendar days. All SAEs will be followed until the Investigator and Sponsor agree the event is satisfactorily resolved or returns to the baseline condition.

Any SAE that is not resolved by the end of the study or upon discontinuation of the patient's participation in the study is to be followed until it either resolves, stabilizes, returns to baseline values (if a baseline value is available), or is shown to not be attributable to the study drug or procedures.

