## 8.6 Prior and Concomitant Illnesses and Medications

### 8.6.1 Prior and Concomitant Illnesses

Investigators should document all prior significant illnesses that the patient has experienced prior to screening. Additional illnesses present at the time when informed consent is given and up to the time of first dosing are to be regarded as concomitant illnesses. Illnesses first occurring or detected during the study and/or worsening of a concomitant illness during the study are to be documented as AEs on the eCRF.

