**Footnotes:**

- a. Informed consent to be obtained before any other study procedures are performed.
- b. Medical history, including previous cancer therapies, cancer history, and past and ongoing concomitant illnesses which are relevant to the disease under study.
- c. A complete physical examination is required at screening and end of study/early termination. Directed physical examinations may be limited to problem focused review of symptoms and major organ systems. This should include an assessment for signs and symptoms of peripheral neuropathy as this is a known adverse event associated with MMAE-based ADCs and may be expected to occur with OBI-999.
- d. Height to be obtained at screening only.
- e. Vital signs include temperature, blood pressure and pulse. Temperature measurement will be obtained as clinically indicated.
- f. Performed by ophthalmologist as follows:
  - Part A - At screening, every 2 cycles for the first 6 months (C2, C4, C6, C8), then every 3 cycles thereafter (C11, C14 and so on), and the end of study/early termination visit.
  - Part B – At screening and at the discretion of the Investigator during the course of the study.
- g. ECOG performance status: at screening, D1 of each cycle, and end of study/early termination
- h. 12-lead ECG with assessment of QTcF: at screening, Cycle 1 Day 1, Cycle 1 Day 3 ( $48\pm 2$  hours after the end of the Cycle 1 Day 1 OBI-999 infusion) and EoS/ET. The ECG testing on C1D4 could be tested 24 hours before but no later than C1D4.
- i. Pregnancy testing should be performed in females of childbearing potential only. A serum pregnancy test is required during screening. A urine or serum pregnancy test is acceptable end of study or early termination
- j. Tumor biopsy samples are mandatory at screening visit. Fresh (preferred) tissue or archival tissue is acceptable. A minimum of 5 slides are required for the central laboratory Globo H assay for determination of eligibility in Part B. Up to 10 unstained additional slides should be provided, depending on availability, for the protocol defined exploratory studies.
- k. Hematology and Serum chemistry (Laboratory Assessments: [Table 12-1](#)). Blood draw is prior to OBI-999 infusion. For C2D1 and each cycle after, laboratory assessments may be drawn 72 hours in an advance of infusion.  

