## 13 Exploratory Analyses

### 13.1 Tumor Tissue Samples

Tumor tissue biopsy or tissue samples will be collected at time of screening in both Part A and Part B of the study. Fresh (preferred) or archival tissue that is less than 10 years old is acceptable. Tumor tissue samples with fewer than 100 tumor cells will be deemed not evaluable. A fine needle aspirate, frozen sample, plastic embedded sample, bone, bone marrow, cell block, clot, cytologic specimen, decalcified sample, or formalin fixed sample that was frozen at any point prior to fixation will not be accepted. All attempts should be made to obtain fresh biopsy specimens. However, if historical sample is available, they should be retained along with histology/pathology report, if possible. All fresh biopsy specimens or historical samples should be sent to the qualified laboratory for testing. A minimum of 5 slides are required for the central laboratory Globo H assay for determination of eligibility for Part B. Up to 10 unstained additional slides should be provided, depending on availability, for testing tumor associated biomarkers as well as conducting a bridging study for the future companion diagnostic test.

The mandated baseline slides are to be used for Globo H testing by IHC to define the level and extent of Globo H expression, as this is the target of OBI-999. The 5 slides required for patients in Part B are part of the eligibility assessments, as all patients in Part B of the study must have a Globo H H-score of  $\geq 100$  to be eligible for study entry.

An analysis will be performed to determine whether there is a potential correlation between baseline tumor Globo H expression as assessed by IHC H-score and response to OBI-999 treatment, as assessed by change from baseline in the sum of diameters of measurable lesions and by RECIST response.

Apart from the mandatory Globo H assessments, up to 10 additional slides have been requested, if available, to identify potential predictive biomarkers for OBI-999 activity such as assessment of expression of additional tumor-associated glycans which may be pathologically associated with Globo H overexpression (e.g., SSEA-3 and SSEA-4) or molecular phenotypes of tumors which may be associated with aberrant Globo H expression.

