- Serious TEAEs related to OBI-999*
- TEAEs leading to death*
- TEAEs leading to discontinuation of OBI-999*
- Serious TEAEs leading to discontinuation of OBI-999*
- TEAEs leading to study discontinuation*
- Serious TEAEs leading to study discontinuation*

Tables by SOC and PT will display the incidence of events (number of events, number and percentage of patients with any event, number of events of each specific SOC, number and percentage of patients with any event of each specific SOC, number of events of each specific PT and number and percentage of patients with any event of each specific PT).

Tables of TEAEs and serious TEAEs by SOC, PT and worst CTCAE grade (per summarization level) will be presented and will display number and percentage of patients with any event of each specific SOC/PT/CTCAE grade. Number of events will not be displayed. If a patient has multiple AEs with the same SOC or SOC and PT respectively and one of them has missing severity, the highest severity will be used. If the severity is missing for all AEs with the same SOC or SOC and PT, a “missing” category will be added in the summary table.

The following listings will be prepared for AEs. Only those AEs marked with * will be listed in the aCSR as per sponsor decision.

- Pre-treatment AEs
- All TEAEs*
- All TESAEs*
- All TEAEs related to OBI-999*
- TEAEs leading to death (with Grade 5 or “Fatal” as an outcome)*
- All TEAEs leading to discontinuation of OBI-999*
- All TEAEs leading to study discontinuation
- Post-treatment AEs

Number and percentage of patients with laboratory abnormalities with grade ≥ 3 will be provided by study part, by cohort (by dose level in Part A and by cancer type in Part B) and by visit.

B. Dose-limiting toxicities (DLTs) with OBI-999*

A DLT is defined as the occurrence of any of the following events, within the first cycle of treatment that is considered to be at least possibly related to OBI-999:

- Grade 4 neutropenia lasting more than 7 days.
- Febrile neutropenia.
- Grade 4 thrombocytopenia.
- Grade 3 thrombocytopenia with \geq Grade 2 bleeding requiring platelet transfusions.
- \geq Grade 3 fatigue, nausea and vomiting or diarrhea for more than 72 hours despite optimal supportive care.
- Any Grade 4 gastrointestinal toxicity.

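### Mandatory SAE reporting and the only dated AE window open at first dose, so a serious complication of a fresh screening biopsy has no mandated report or timeline

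*Protocol*

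**What the plan says.** **SAE reporting.** Protocol 12.5.3 defines the reportable event as "An SAE occurring during the study from the first dose of study treatment (Cycle 1 Day 1", with the window closing 28 days after treatment stops. Reports are due within 24 hours, whatever the cause. The end of that section allows for an SAE being attributable to study procedures as well as to the drug.

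**AE collection.** Protocol 12.5.1 says that "treatment emergent AEs will be collected starting from the time the patient receives the first dose of study drug", running to 28 days after the last dose. That sentence is worded for treatment-emergent events only. Earlier in the section, after describing the history taken at screening, it says: "Changes in these conditions and new symptoms, physical signs, syndromes, or diseases should be noted on the AE eCRF during the rest of the study".

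**Pre-dose illness.** Protocol 8.6.1 says that additional illnesses present at consent and "up to the time of first dosing are to be regarded as concomitant illnesses". Its next sentence sends illnesses that first occur or are detected during the study to the AE eCRF.

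**Tissue.** Table 9-1 schedules the tumor biopsy at screening only. Its footnote j reads: "Tumor biopsy samples are mandatory at screening visit. Fresh (preferred) tissue or archival tissue is acceptable". Section 13.1 adds "All attempts should be made to obtain fresh biopsy specimens" and accepts archival tissue less than 10 years old.

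**Consent.** Protocol 9.1 allows an optional, separate pre-screening consent for Globo H testing in Part B.

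**Reporting.** SAP 10.7.1 includes "Pre-treatment AEs" among its AE listings, but without the asterisk that marks what will be produced for the abbreviated CSR (aCSR).

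**The concern.** The only protocol-scheduled biopsy falls before either dated window opens. If a patient bleeds, perforates or becomes infected after a biopsy taken for the study, 12.5.3 does not require the site to tell the sponsor, and no clock runs. Several other sentences could bring the event onto a form, but they point to different forms and none sets a deadline.

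What is at stake is harm from a study procedure. It might be recorded at one site as an AE, at another as background illness, and at a third perhaps not at all, and no starred aCSR output would show it. Patients who are tested and never dosed are the extreme case, because a window that opens at first dose never opens for them.

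**Working it through.** **1. Timing.** Tissue is obtained at screening, Day -28 to -1 in Table 9-1, or possibly earlier under the pre-screening consent. The SAE window and the dated AE window open at Cycle 1 Day 1. The two periods do not overlap.

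**2. Possible routes for a complication after a fresh study biopsy and before first dose.**

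| Route | Source | Mandated, with a timeline? | Reaches the aCSR? |
|---|---|---|---|
| SAE report | Protocol 12.5.3 | No; the window is not open | No required pre-dose report exists to feed it |
| AE eCRF | Protocol 12.5.1, sentence on new symptoms; 8.6.1, second sentence | Recording only; no start date, no deadline | No. The starred AE listings are treatment-emergent; SAP Appendix II classes a known onset before study drug as not a TEAE; the pre-treatment listing is unstarred |
| Concomitant illness | Protocol 8.6.1, first sentence | No | No. SAP 11 drops medical history, current conditions and other medical history |

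The second and third routes both have textual support, which is the conflict. No route in the table is both mandated and reported.

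**3. Who may need fresh tissue.** Inclusion criterion 8 in Protocol 7.1.1, footnote j and section 13.1 all accept archival material, so a tissue sample is mandatory and a new biopsy is not. Section 13.1 does reject fine needle aspirates, cell blocks, cytologic specimens, bone and decalcified samples. Cohort 3 admits cytologically confirmed patients, so one who has only cytologic material would need new tissue to enter Part B.

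**4. Patients tested and never dosed (Part B only).** Part A required no Globo H result for entry.

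Inputs, from Protocol Figure 4-1: H-score of at least 100 in 32.4% of 139 pancreas specimens and 20.9% of 191 colon specimens. These percentages fit whole counts: 45/139 = 32.4% and 40/191 = 20.9%. The counts are back-calculated, because the figure does not give them. Nine patients per cohort in stage 1 comes from Protocol 14.1.

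Formulas: ineligible share = 1 - prevalence; expected number tested = places / prevalence.

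| | Pancreas | Colon |
|---|---|---|
| Ineligible share | 1 - 0.324 = 67.6% | 1 - 0.209 = 79.1% |
| Tested to fill 9 | 9/0.324 = 27.8, about 28 | 9/0.209 = 43.1, about 43 |
| Of these, never dosed | 28 - 9 = 19 | 43 - 9 = 34 |

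For these two cohorts together, about 71 patients would be tested and 53 never dosed. Filling all 19 places would need about 59 (19/0.324 = 58.6) and 91 (19/0.209 = 90.9), but SAP 5.4 says the formal go/no-go analysis never happened. No tumor type in Figure 4-1 reaches 50% positive (the highest is lung adenocarcinoma at 48.9%), so any basket drawn from the listed types would also be mostly negative.

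**5. Number exposed to the gap.** This is the number tested multiplied by the share having a fresh biopsy. The documents do not give that share. Over its full range of 0 to 1, stage 1 of the two cohorts gives 0 to about 71 fresh biopsies. No complication rate is given, so no number of harmed patients can be derived.

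**The case against.** A reader might infer that biopsy complications go unreported and that undosed patients have no reporting route at all. The documents do not support that. The dated sentence in 12.5.1 is confined to treatment-emergent events. Another sentence in the same section sends new symptoms to the AE eCRF with no first-dose limit. The second sentence of 8.6.1 does the same, and on a plain reading its first sentence may not cover an illness that was absent at consent. The SAP's pre-treatment listing and its not-TEAE rule in Appendix II both presuppose pre-dose AE records. This stands: it shows inconsistent rules, not a proven absence of data.

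Two further inferences should be resisted. One is that every patient must undergo a biopsy; archival tissue is accepted. The other is that most patients tested had an invasive procedure under the pre-screening consent. Section 9.1 says only that the consent is for Globo H testing, which fits archival slides equally well.

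On impact, the primary objective concerns the tolerability of OBI-999 itself. The Safety Review Committee's stated Part B task is toxicity at the recommended dose, and it includes the investigators, so it cannot be said that the committee would be unaware of a biopsy problem. That also stands.

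None of this supplies a mandated report or a deadline for a serious pre-dose event.

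**Conclusion.** The point holds in a limited form. A serious complication of a fresh screening biopsy has no required report and no timeline, and Protocol 8.6.1, 12.5.1 and 12.5.3 and SAP 10.7.1 need reconciling on how any pre-dose event is recorded. The gap is clearest for Part B patients who sign only the pre-screening consent. No safety recording is described for them, and the disposition table in SAP 10.4 counts only those who signed the main consent.

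The expected ineligible shares, about 68% for pancreas and 79% for colon, assume that trial patients resemble the specimens in Figure 4-1. They count patients tested, not biopsied or harmed, and the documents give no actual screen-failure count. Treatment-emergent safety summaries and the response analysis are unaffected. The gap should be closed, but it does not threaten the trial's main conclusions.

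**What to change.** **Protocol wording, if enrolment resumes or the text is reused.** In 12.5.1 and 12.5.3, collect SAEs, and AEs related to protocol-required procedures, from the first study consent (including the Globo H pre-screening consent) to first dose or screen failure. Keep first dose as the start of the TEAE definition. Amend 8.6.1 so that a procedure-related event after consent is an AE and not a concomitant illness.

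**This trial.** SAP 3 records that the sponsor stopped the study on 10 November 2023, so a protocol change can no longer capture screening events. Star the pre-treatment AE listing in SAP 10.7.1 so that any pre-dose AEs recorded appear in the aCSR. State there that pre-dose procedure-related events had no mandated collection. The statement is needed even if the listing is empty, because an empty listing would not show that no events occurred.

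**Cost.** A few extra pre-dose reports for sites on the existing AE and SAE forms, and one extra listing that the SAP already names.
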